6.2.2 Dose interruption or dose reduction

For patients who do not tolerate the protocol-specified dosing schedule, dose adjustments are permitted in order to allow the patient to continue the study treatment. The following guidelines need to be applied: for all patients who are receiving INC424, there are mandatory dose decreases or dose interruptions for declining platelet counts or ANC levels that might be observed while on INC424 therapy. In addition to mandatory dose interruption or decrease for hematologic toxicities, there are mandatory criteria for permanent discontinuation of INC424 (See [Section 6.2.6](#)).

Dosing must be held if platelet counts decline below 50,000/ μ L (Grade 3 laboratory abnormality by CTCAE v. 3.0, or if ANC falls below 500/ μ L while receiving INC424.

6.2.2.1 Dose interruption or dose reduction for patients starting INC424 at doses of 15 – 20 mg p.o. BID

Doses should be decreased for platelet count values < 125,000/ μ L as shown in [Table 6-2](#) with optional restarting or resuming prior dose after recovery ([Section 6.2.3](#)). In order to provide sufficient data to make the dose adjustment decisions, it is recommended that hematology parameters be obtained at least weekly for platelet count <100,000/ μ L or ANC < 1000/ μ L and at least two times weekly for platelet count < 50,000/ μ L or ANC < 500/ μ L.

These changes must be recorded on the Dosage Administration Record eCRF.

Table 6-2 Dose reductions in INC424 for safety in patients with platelet count declines (for those starting on INC424 dose of 15 – 20 mg p.o. BID)

[figure not shown]
Platelet Count at Time of Decline	Dose at the Time of Platelet Decline				
	25 mg BID	20 mg BID	15 mg BID	10 mg BID	5 mg BID
Dose that MUST be Instituted					
≥ 125,000/ μ L	No dose reduction required				
100,000/ μ L to < 125,000/ μ L	20 mg BID	20 mg BID	15 mg BID	10 mg BID	5 mg BID
75,000/ μ L to < 100,000/ μ L	10 mg BID	10 mg BID	10 mg BID	10 mg BID	5 mg BID
50,000/ μ L to < 75,000/ μ L	5 mg BID	5 mg BID	5 mg BID	5 mg BID	5 mg BID
< 50,000/ μ L	Stop Dosing				

6.2.2.2 Dose interruption or dose reduction for patients starting INC424 at doses of 5 mg p.o. BID

Dose modifications are made according to the platelet count as follows (see [Table 6-3](#)):

- If platelets > 25,000 - < 50,000/ μ L: reduce the INC424 dose by 5 mg o.d.
- If platelets ≤ 25,000/ μ L: hold treatment. Treatment can be restarted at a later date if platelets increase to ≥ 50,000/ μ L.

The patients should then be reassessed the following month. If the platelet count improves, the patient can restart treatment, and if the platelet count does not improve the patient should be withdrawn from the study.

These changes must be recorded on the DAR eCRF.

Table 6-3 Dose reductions in INC424 for safety in patients with platelet count declines (for those starting on INC424 dose of 5 mg PO BID)

Platelet count at time of decline	Dose reduction/hold
≥50,000/µL	No dose reduction required
< 50,000/µL and > 25,000/µL	Decrease dose by 5 mg OD
≤25,000/µL	Hold treatment; treatment may be restarted once the platelet count increases to >50,000/µL as outlined in Section 6.2.3.2

Study drug MAY be permanently discontinued for a Grade 4 clinical event that has NOT been confirmed upon rechallenge with the study drug, at the option of the Investigator.

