	
following conditions are met:
 
- Palpable spleen length below the costal margin that has been reduced by < 40% at the Week 4 visit relative to baseline.- Platelet count at the Week 4 blood draw is > 150,000/μL and platelet count has never been < 150,000/μL at a prior laboratory assessment while receiving INC424 (Figure 6-1).- ANC levels have remained \geq1000/μL since enrollment in the study. 
Additional dose increases beyond the week 4 dose escalation for patients who start on 15 – 20 mg BID of INC424 are permitted, at the discretion of the investigator, as follows:
 
- The patient must not have had a prior safety-related dose reduction.- The patient must have had a platelet count \geq 150,000/μL at every assessment since baseline.- The patient must have had ANC \geq 1000/μL at every assessment since baseline.- The dose increase may only be an increase of 5 mg BID.- The total dose may never exceed 25 mg BID. 
For those patients who start INC424 treatment at a dose of 5 mg BID, dose increases can be made, at the discretion of the investigator, as described below. The dose can be escalated 5 mg once a day starting at week 4, and thereafter no more than every two weeks ONLY if:
 
- The patient must not have had a prior safety-related dose reduction.- Platelet count remains \geq 50,000/μL since last lab scheduled visit.- ANC $>$ 1000/μL since last scheduled visit.- No dose reduction or interruption for safety occurred in the preceding weeks after the last planned visit.- The dose increase may only be an increase of 5 mg o.d. i.e., from 5 mg PO BID to 5 mg QAM and 10 mg QPM.- The total dose may never exceed 25 mg BID. 
Following a dose increase, platelet count and ANC levels should be assessed approximately 2 weeks after the dose adjustment. If a regularly scheduled Study Visit does not coincide with this required blood draw, an unscheduled Interim Visit should be held to collect samples for hematology.
 
Dose interruption or dose reduction (Section 6.2.2) is mandatory as follows for patients who start on dose of 15 – 20 mg BID:
 
Dosing must be held if platelet counts decline to < 50,000/μL (Grade 3 laboratory abnormality by CTCAE v. 3.0, or if ANC falls below 500/μL while receiving INC424.
 
Doses should be decreased for platelet count values < 125,000/μL as shown in Table 6-2 with optional restarting or resuming prior dose after recovery Section 6.2.3 In order to provide sufficient data to make dose adjustment decisions, it is recommended that hematology parameters be obtained at least weekly for platelet count <100,000/μL or ANC < 1000/μL and at least two times weekly for platelet count < 50,000/μL or ANC <500/μL.
 
Dose interruptions or dose reductions for patients starting INC424 5 mg BID: dose

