6.2.6 Dose interruption and discontinuation of study drug

[figure not shown]
In some circumstances, it may be necessary to temporarily interrupt treatment as a result of adverse drug reaction that may have an unclear relationship to study drug. Except in cases of emergency or for protocol mandated holds for ANC or platelet count, it is recommended that the investigator consult with the Sponsor medical monitor (or other representative of the Sponsor) before temporarily interrupting therapy. Study drug may be held by the investigator at any time if there is concern about patient safety, and for all aspects of the conduct of the protocol the safety of the individual patient is paramount. Treating investigators may employ any means necessary to ensure patient safety, particularly in medical circumstances not anticipated by this protocol. Additionally, the investigator must obtain approval from the Sponsor before restarting study drugs that were temporarily discontinued for an adverse experience.

Dosing must be halted immediately if any of the following occur for patients starting with 15 & 20 mg BID:

- Platelet counts fall below 50,000/ μ L
- ANC levels fall below 500/ μ L
- Hemoglobin cannot be maintained \geq 6.5 g/dL despite the use of transfusion therapy

Dosing may be reinstated following dose holding using the re-start schema detailed in [Section 6.2.3](#). In order to provide sufficient data to make the dose adjustment decisions, it is recommended that hematology parameters be obtained at least weekly for platelet count $<$ 100,000/ μ L or ANC $<$ 1000/ μ L and at least two times weekly for platelet count $<$ 50,000/ μ L or ANC $<$ 500/ μ L. (Note: patients with platelet counts of $<$ 10,000/ μ L should be hospitalized, unless local or national practice does not permit it).

If a patient on a dose-hold requires frequent testing for safety parameters, these tests may be performed at a local laboratory. If the study drug is interrupted for any reason for more than 8 weeks, dosing may not be restarted, except in the case of splenectomy, for which a maximum 12 week period of study drug interruption is permitted. Although study guidelines provide for dose reduction/interruption for the management of hematologic or non-hematologic toxicities that occur during the course of the study, the following guidelines should be used to determine whether permanent discontinuation of study drug is necessary.

Discontinuation of study drug for hematologic toxicity:

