Study drug MUST be permanently discontinued if the lowest allowed dose (5 mg BID or 5 mg QD with concomitant CYP3A4 inhibitor) is not tolerated due to the following:

- Platelets cannot be maintained $\geq 50,000/\mu\text{L}$.
- Absolute neutrophil count cannot be maintained $\geq 500/\mu\text{L}$.
- Hemoglobin cannot be maintained $\geq 6.5 \text{ g/dL}$ despite the use of transfusion therapy.

In the event that any patient permanently discontinues the study drug, regardless of reason, reasonable efforts should be made to have the patient return for an early termination visit and have the End of Treatment evaluations completed as described in [Section 7.6](#) and [Section 7.6.2](#). The site is requested to provide voluntary follow-up of all withdrawn patients, with regard to incidence of leukemia or death.

The date the patient discontinued the study drug and the specific reason for discontinuation will be recorded in the eCRF. This will include reasons such as discontinued due to disease worsening or withdrawn due to adverse event. This information will be used to summarize the reasons for study withdrawal.

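### The opening of protocol Section 6.2.2 holds dosing below 50,000/µL without limiting the rule to 15–20 mg BID starters, which conflicts with Table 6-3 for 5 mg BID starters; Section 6.2.6 also omits this group's 5 mg once-daily floor

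*Protocol*

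**What the plan says.** Section 6.2.2 of the protocol opens with a general statement: "for all patients who are receiving INC424, there are mandatory dose decreases or dose interruptions for declining platelet counts or ANC levels". Its next paragraph, still ahead of the split by starting dose, says "Dosing must be held if platelet counts decline below" 50,000/µL, or if ANC falls below 500/µL.

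The text then divides. For 5 mg BID starters with platelets above 25,000 and below 50,000/µL, Section 6.2.2.2 says "reduce the INC424 dose by 5 mg o.d" and Table 6-3 says "Decrease dose by 5 mg OD". Both reserve the hold for counts of 25,000/µL or less.

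Two other places give the 50,000/µL hold with a limit on who it covers:
- Synopsis, Dose, regimen, treatment: "Dose interruption or dose reduction (Section 6.2.2) is mandatory as follows for patients who start on dose of 15" to 20 mg BID. It then gives 5 mg BID starters the 25,000/µL rule.
- Section 6.2.6: "Dosing must be halted immediately if any of the following occur for patients starting with 15 & 20 mg BID".

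On the lowest dose, Section 6.2.6 says "Study drug MUST be permanently discontinued if the lowest allowed dose (5 mg BID or 5 mg QD with concomitant CYP3A4 inhibitor") is not tolerated, for example because platelets cannot be kept at 50,000/µL or more. That sentence has no starting-dose limit. Section 6.2.3.2 restarts 5 mg BID starters at 5 mg once daily, and Section 7.6.1 adds patients with baseline platelets of 50,000 to <100,000/µL to its lowest-dose wording.

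**The concern.** A site with a 5 mg BID starter at, say, 40,000/µL finds a mandatory hold in one part of Section 6.2.2 and a reduction in another. The wider text does not steer it to the right one. The dose-increase rules for this same group (6.2.1.2), the on-treatment section (7.5) and the Week 4 visit (7.5.1.3) all point to Section 6.2.2 as a whole, not to 6.2.2.2.

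A wrong hold is the cautious error for bleeding, but it has a cost. Section 6.2.3.2 requires platelets of at least 50,000/µL to restart. Section 6.2.6 bars a restart after more than 8 weeks off drug, except after splenectomy. Section 6.2.5 notes that symptoms may return within about a week of stopping. A patient held in error whose count does not recover could lose treatment that Table 6-3 would have continued at a lower dose.

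The lowest-dose wording in Section 6.2.6 adds to this. Read literally, it ends treatment for a patient who cannot keep 50,000/µL on 5 mg BID, at the point where Table 6-3 calls for 5 mg once daily.

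**Working it through.** There is no stated figure to reproduce. The check sets the rules side by side and converts doses to mg/day.

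**Step 1: platelet rule for 5 mg BID starters.**

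| Platelets (/µL) | Opening of 6.2.2 | 6.2.2.2 and Table 6-3 | Result |
|---|---|---|---|
| 50,000 or more | no action | no action | agree |
| above 25,000, below 50,000 | hold | reduce by 5 mg once daily | conflict |
| 25,000 or less | hold | hold | agree |

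**Step 2: at which doses the conflict matters.** Take a count inside the middle band. A hold gives 0 mg/day.
- On 5 mg BID (2 × 5 = 10 mg/day), reduction gives 10 − 5 = 5 mg/day. This differs from a hold.
- On 5 mg morning and 10 mg evening (15 mg/day, the first permitted increase), reduction gives 15 − 5 = 10 mg/day. This differs from a hold.
- Already on 5 mg once daily, reduction gives 5 − 5 = 0 mg/day. This is the same as a hold.

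So the conflict is confined to 5 mg BID starters taking at least 10 mg/day.

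**Step 3: which rule was intended.** The synopsis cites Section 6.2.2 by number and attaches the 50,000/µL hold to 15–20 mg BID starters only. The halt list in Section 6.2.6 is limited in the same way. Both agree with Table 6-3. The opening of 6.2.2 is the statement that lacks the limit.

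**Step 4: lowest dose.**
- Section 6.2.6 without a CYP3A4 inhibitor: 2 × 5 = 10 mg/day.
- First Table 6-3 reduction from the starting dose: 10 − 5 = 5 mg/day.
- Section 6.2.3.2 restart: 5 mg/day.
- Ratio: 5 / 10 = 0.5.

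The dose that the protocol assigns to this group by design is half the minimum in Section 6.2.6.

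**Step 5: ANC.** The hold below 500/µL appears in Section 6.2.2, in the synopsis for both groups, and in Section 6.2.3.2. There is no conflict.

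**Step 6: analysis.** SAP Section 3.2 summarises exposure, interruptions and reductions from the dose records. The per-protocol exclusions in SAP Section 2.1 concern age, unconfirmed diagnosis and fibrosis grade. None concerns dosing.

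**The case against.** The strongest reply is that the intended rule can be found. The reference to all patients introduces a general statement, and the hold sentence sits in a separate paragraph. Section 6.2.2.2 and Table 6-3 are headed for 5 mg BID starters, and a specific rule is normally read as governing a general one. The synopsis and the Section 6.2.6 halt list point the same way. On the lowest dose, Section 7.6.1 presents itself as spelling out the Section 6.2.6 criteria and includes the low-platelet group. Section 6.2.4 goes lower still, to 5 mg every other day for someone already on once-daily dosing who adds a potent CYP3A4 inhibitor.

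Most of this stands, and it sets the scale: these are wording errors with a recoverable intent, not a flawed dosing design. It does not remove them. Section 6.2.2 calls its rules mandatory and does not say that its subsections override the opening. The discontinuation rule in 6.2.6 has no starting-dose limit, and 6.2.2 sends readers to it for permanent discontinuation. A site should not have to reconcile four places to decide whether to stop drug.

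A reader might also infer two contradictory withdrawal tests: Section 6.2.2.2 says that after a month "if the platelet count does not improve the patient should be withdrawn from the study", whereas 6.2.6 and 7.6.1 ask whether 50,000/µL can be maintained. The documents do not support that. The 6.2.2.2 sentence follows the hold instruction and speaks of restarting, so it naturally concerns patients whose drug was stopped. Restart in 6.2.2.2, Table 6-3 and 6.2.3.2 is tied to about the same 50,000/µL. Applying the sentence to a patient still taking 5 mg once daily, and counting any rise as improvement, adds two steps that are not in the text. It also overlooks that a further 5 mg reduction would already bring that patient to zero.

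**Conclusion.** The protocol is wrong as written in two places, both affecting 5 mg BID starters.

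- The platelet hold at the opening of Section 6.2.2 lacks its limit to 15–20 mg BID starters. It conflicts with 6.2.2.2 and Table 6-3 above 25,000 and below 50,000/µL, for patients on at least 10 mg/day. Reduction is the intended rule.
- The discontinuation rule in Section 6.2.6 sets a minimum of 10 mg/day without a CYP3A4 inhibitor. It omits the 5 mg/day that Table 6-3, 6.2.3.2 and 7.6.1 provide for.

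The reading of intent rests on the synopsis, the 6.2.6 halt list and 7.6.1, which agree with one another. The documents do not give the number of 5 mg BID starters, so the number affected cannot be stated.

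A reader might infer a bias in the results. None follows: exposure is described as recorded, no dosing deviation removes a patient from the per-protocol set, and no hypothesis is tested. Nor do these errors put patients at greater bleeding risk, since a site misled by Section 6.2.2 holds drug. The issue is consistent dosing and avoidable loss of treatment in the low-platelet group, and it is worth correcting for that reason.

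**What to change.** - In Section 6.2.2, limit the platelet hold below 50,000/µL to patients who start at 15–20 mg BID, and keep the ANC hold below 500/µL for everyone.
- In the Section 6.2.6 discontinuation rule, add 5 mg once daily as the lowest allowed dose for patients who start at 5 mg BID, matching Section 7.6.1.

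The cost is one clause and one phrase, carried through a written amendment with the approvals that Section 12.11 requires, and a notice to sites. No new data or analysis is needed. Enrollment closed on 31 December 2014, so the change reaches only treatment remaining before the last visit planned for December 2016.

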--	---

	
interruptions are made according to the platelet count as follows (see Table 6-2 and Table 6-3):
 
 - If platelets \leq 25,000/μL and/or ANC $<$ 500/μL: hold treatment - If platelets $>$ 25,000 - $<$ 50,000/μL: reduce the INC424 dose by 5 mg o.d. increments 
The patients should then be reassessed the following month. If the platelet count improves, the patient can restart treatment, and if the platelet count does not improve the patient should be withdrawn from the study

Dose, regimen, treatment, continued	
The dose strategy in Table 6-4 covers the starting doses (15 mg BID and 20 mg BID) and possible doses after an increase for inadequate efficacy (20 mg BID and 25 mg BID).
 
Patients are free to withdraw consent and discontinue participation in the study at any time, without prejudice to further treatment. A patient's participation in the study may also be discontinued at any time at the discretion of the Investigator or Sponsor. The following are reasons the Investigator or Sponsor may remove a patient from the study:
 
 - The patient requests discontinuation. - The Investigator thinks a change of therapy would be in the best interest of the patient. - The patient experiences an intolerable AE. - The patient is found to be not eligible for further study treatment. - The patient is non-compliant with study requirements. - The patient becomes pregnant during the study or if a patient fails to use adequate birth control (for those patients who are able to conceive). - The patient requires a medication prohibited by the protocol.
Supply, preparation, and administration	INC424 is provided as a 5 mg or 10 mg tablet. The bottles are labeled in the local language. Once commercially available, the drug may be provided locally. The study medication is referred to as INC424 5 mg or 10 mg tablet on the label. INC424 is to be administered orally, without regard to food, in an outpatient setting in accordance with specified dosing schedules. The bottles of tablets should be stored at room temperature, 15°C to 30°C (59°F to 86°F).
Visit schedule and assessments	Refer to Table 7-1 in protocol.

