6.2.3 Restarting or reinstating previous dose

6.2.3.1 Restarting or reinstating previous dose for patients who start INC424 15 – 20 mg BID

Dosing of INC424 may be restarted or increased following recovery of platelet counts and/or ANC to acceptable levels as illustrated in [Table 6-4](#) for those patients who start on INC424 15 – 20 mg BID. The objective for restarting or escalating after a reduction for safety is to find the highest safe dose of INC424 for each patient, with increases in dose generally not more than in increments of 5 mg BID and not more often than every 2 weeks. Patients who are restarting after a reduction for thrombocytopenia may not receive doses above 20 mg BID maximum. Similarly, ANC levels that decline to < 500/ μ L necessitate immediate dose interruption ([Section 6.2.6](#)). ANC level recovery to 500 / μ L and above but less than 750/ μ L will allow dosing to be restarted at 5 mg BID, and ANC levels between 750/ μ L, but < 1000/ μ L may restart at 10 mg BID. Absolute neutrophil count level increases to above 1000/ μ L will allow a further dose increase to a maximum of 20mg BID.

The maximum dose used should never exceed 5mg BID LESS than any dose that resulted in platelets falling below 100,000/ μ L or ANC falling below 500/ μ L. After restarting using the guidelines in [Table 6-4](#), if it is found that a patient cannot tolerate the lowest allowed dose (5mg BID, or 5mg QD with concomitant CYP3A4 inhibitor, see [Section 6.2.4](#)) without platelets falling below 50,000/ μ L, neutrophils falling below 500/ μ L, or Hgb falling below 6.5g/dL despite the use of transfusion therapy, drug must be permanently discontinued ([Section 6.2.6](#), and [Section 7.6.1](#)).

Table 6-4 **Restarting or increasing INC424 dose after safety interruptions or dose reductions for patients starting on doses of 15 – 20 mg BID**

Current Platelet Count	Dose Restart or Dose Increase Guidelines
< 50,000/ μ L	Continue hold
50,000/ μ L to < 75,000/ μ L	5 mg BID for at least 2 weeks; if stable, may increase to 10 mg BID
75,000/ μ L to < 100,000/ μ L	10 mg BID for at least 2 weeks; if stable, may increase to 15 mg BID
100,000/ μ L to < 125,000/ μ L	15 mg BID
\geq 125,000/ μ L	20 mg BID
Current ANC Level	Dose Restart or Dose Increase Guidelines
< 500/ μ L	Continue hold
500 to < 750/ μ L	5 mg BID for at least 2 weeks; if stable, may increase to 10 mg BID
750 to < 1000/ μ L	10 mg BID for at least 2 weeks; if stable, may increase to 15 mg BID

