1000 to < 1500/ μ L	15 mg BID for at least 2 weeks; if stable may increase to 20 mg BID
\geq 1500/ μ L	20 mg BID

NOTE: Whether the dose interruption occurred because of neutropenia, thrombocytopenia or both, when restarting, both the platelet count and ANC must be considered to determine the restart dose, with the lower calculated dose being used.

6.2.3.2 Restarting or reinstituting previous dose for patients who start INC424 at 5 mg BID

Dosing of INC424 may be restarted or increased following recovery of the platelet count to $\geq 50,000/\mu\text{L}$. Reinitiate treatment at a dose of 5 mg o.d. The dose may be increased by 5 mg o.d. every two weeks based on platelet counts and the absence of other adverse events.

When the ANC is $< 500/\mu\text{L}$, hold INC424 dosing. INC424 can be reinitiated in this population once the ANC is $\geq 500/\mu\text{L}$, at a dose of 5 mg o.d. The dose may be increased by 5 mg o.d. every two weeks based on platelet counts and the absence of other adverse events.

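### For patients starting at 5 mg BID, the platelet hold in protocol 6.2.2 and the dose floor in 6.2.6 contradict the rules written for that group

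*Protocol*

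**What the plan says.** **Hold rule.** Protocol 6.2.2 introduces mandatory decreases and interruptions for all patients receiving INC424. Before its subsections by starting dose it says "Dosing must be held if platelet counts decline below 50,000"/µL, or if ANC falls below 500/µL. Section 6.2.2.2, headed for patients starting at 5 mg BID, says for counts >25,000 to <50,000/µL to "reduce the INC424 dose by 5 mg o.d". It calls for a hold only at ≤25,000/µL. Table 6-3 repeats this: "Decrease dose by 5 mg OD" in the middle band.

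The synopsis (Dose, regimen, treatment) limits the <50,000/µL hold by starting dose: "Dose interruption or dose reduction (Section 6.2.2) is mandatory as follows for patients who start on dose of 15"–20 mg BID. For 5 mg BID starters in the middle band it says "reduce the INC424 dose by 5 mg o.d. increments". The immediate-halt list in 6.2.6 is likewise confined to 15 and 20 mg BID starters.

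**Dose floor.** Section 6.2.6 states: "Study drug MUST be permanently discontinued if the lowest allowed dose (5 mg BID or 5 mg QD with concomitant CYP3A4 inhibitor") is not tolerated because platelets, ANC or hemoglobin cannot be kept above their limits. It makes no exception for low-platelet patients. Yet 6.2.3.2, for 5 mg BID starters, says after recovery "Reinitiate treatment at a dose of 5 mg o.d". Section 7.6.1, which presents itself as spelling out the 6.2.6 criteria, inserts low-platelet patients (50,000 to <100,000/µL) into the same parenthesis. It therefore appears to allow them 5 mg once daily. The floor as worded in 6.2.6 also appears in 6.2.3.1 ("if it is found that a patient cannot tolerate the lowest allowed dose (5mg BID, or 5mg QD with concomitant CYP3A4 inhibitor"), but under a heading limited to 15–20 mg BID starters.

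**The concern.** Both sentences are mandatory, and neither can be followed together with the rules for this group. At 40,000/µL, 6.2.2 stops the drug while Table 6-3 continues it at a lower dose. At 5 mg BID with platelets that will not stay at or above 50,000/µL, 6.2.6 ends treatment while Table 6-3 still has a step to 5 mg once daily.

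The choice matters to the patient. Section 6.2.5 warns that myelofibrosis symptoms may return about a week after interruption. Under 6.2.6 an interruption of more than 8 weeks bars restarting (12 weeks are allowed for splenectomy). A reduction starts no such clock. Under the 6.2.6 floor a patient may leave treatment permanently one dose step early. Sections 12.2 and 12.10 permit no authorized deviations, so a site following either rule departs from the other.

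There is also a reporting consequence. Dose reductions and interruptions are summarized outputs (protocol 11.4), and protocol section 11 displays data by low and non-low baseline platelets. Site-to-site differences in reading the rule would therefore fall in one display group.

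**Working it through.** The plan gives no figure to reproduce. The check applies each rule to a 5 mg BID starter who takes no CYP3A4 inhibitor.

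**Step 1: platelet bands**

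| Platelets (/µL) | 6.2.2 general sentence | 6.2.2.2 and Table 6-3 | Result |
|---|---|---|---|
| ≥50,000 | no hold | no reduction | agree |
| >25,000 to <50,000 | hold | reduce by 5 mg once daily | conflict |
| ≤25,000 | hold | hold | agree |

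The hold conflict is confined to the middle band.

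**Step 2: lowest allowed dose**

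- 6.2.6 floor: 2 × 5 mg = 10 mg/day.
- Next Table 6-3 step from 5 mg BID: 10 − 5 = 5 mg/day.
- Restart dose in 6.2.3.2: 5 mg/day.
- Ratio to the floor: 5/10 = 0.5.

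So Table 6-3 and 6.2.3.2 both prescribe a dose that 6.2.6 treats as not available. This part arises only when the count cannot be maintained, not on a single low value, and only for patients already down to 5 mg BID.

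**Step 3: does the ≥50,000/µL trigger in 7.6.1 undo this?** Section 7.6.1 keeps that trigger, so it supports the lower dose floor but not the 25,000/µL hold threshold. Once the floor is 5 mg once daily the trigger is compatible with Table 6-3: from 5 mg/day the next step is 5 − 5 = 0 mg/day, which is no dose at all.

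**Step 4: how the SAP counts one event.** Take a patient on 5 mg BID whose count falls to 40,000/µL. SAP 3.2 defines an interruption as a zero-dose record between two non-zero records, and a reduction as a move to a smaller daily dose. Its first worked example counts a halt followed by a lower dose as one of each.

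- Table 6-3 path: 10 → 5 mg/day. One reduction, no interruption.
- 6.2.2 hold, then 6.2.3.2 restart: 10 → 0 → 5 mg/day. One interruption and one reduction.

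**The case against.** The strongest reply is that a specific rule overrides a general one. Section 6.2.2 is divided by starting dose, 6.2.2.2 is headed for exactly these patients, and reading the general hold as controlling would leave the middle row of Table 6-3 with no use. The synopsis and the 6.2.6 halt list point the same way. On the floor, 7.6.1 introduces its list as a specification of 6.2.6, so it could be said to supply the missing exception.

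This establishes what was probably intended, but the protocol never says that the specific rule prevails. The general sentence is mandatory, under an all-patients lead-in, with no exception. For the floor the argument is weaker, because 6.2.6 has no subsection for 5 mg BID starters to appeal to. A restatement in 7.6.1 that differs from 6.2.6 is itself an inconsistency.

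Three limiting points do stand:

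- After its platelet bullets, 6.2.2.2 calls for reassessment the following month and withdrawal if the count has not improved. The reduced-dose route is therefore not open-ended, and the treatment difference lies mainly in that month and in patients who improve.
- The SAP tables are descriptive and would correctly record what each patient received. The problem is the variable practice behind the counts, not the counting.
- Enrollment closed on 31 December 2014, so only 5 mg BID starters still on drug are exposed. Last patient last visit was planned for December 2016, so the wording could still govern patients on treatment.

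**Conclusion.** The inconsistency holds in both parts and should be fixed. The hold conflict reaches any 5 mg BID starter with a count >25,000 to <50,000/µL. The floor conflict reaches those at 5 mg BID whose platelets cannot be maintained, where the two sets of rules differ by a factor of two in the lowest dose (10 versus 5 mg/day). Both unqualified sentences err toward less drug, so the harm is unnecessary interruption or early discontinuation and uneven practice between sites, not overdosing.

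The primary endpoint definition, analysis sets and planned methods are unaffected. The number of patients concerned is not in the documents and cannot be derived from them. The conclusion about intent rests on the synopsis, the 6.2.6 halt list, 6.2.3.2 and 7.6.1. Of these, 7.6.1 is the least clearly worded.

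**What to change.** 1. In 6.2.2, limit the platelet part of the hold sentence to patients starting at 15–20 mg BID, as the synopsis does, and refer 5 mg BID starters to Table 6-3. The last row of Table 6-2 already stops dosing below 50,000/µL for the higher-dose starters, so they lose no protection.
2. Keep the ANC <500/µL hold in that sentence for all patients. The 6.2.2.2 bullets and Table 6-3 contain no ANC hold, while the synopsis and 6.2.3.2 show that it applies to 5 mg BID starters.
3. In 6.2.6, name 5 mg once daily as the lowest allowed dose for 5 mg BID starters, and use identical wording in 7.6.1.

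The cost is protocol wording in three sections, with no additional data.
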